### 3.5.4.9. Safety

#### 3.5.4.9.1. Adverse Event

Every observed and reported adverse event, regardless of the causal relationship with the study drug, must be recorded on an adverse event section in case report forms. The query pattern of experience of adverse event to the subjects is as follow;

Patients who are prescribed with INLYTA® for the first time during the study period: “Have you had any health problem since last visit?”

Patients who are already on INLYTA® at the time of enrollment: all safety information will be collected from medical chart since the date of treatment initiation.

For adverse events repeating before and after administrating the study drug, record the date adverse event was first experienced and the date adverse event resolved. Background information on INLYTA® can be obtained from the current version of the local product document, which is the single reference safety document (SRSD) for information relating to INLYTA®.

Check either ‘yes’ or ‘no’ in adverse event section. If ‘yes’, record in detail.

- Adverse events: Record the name of adverse event. If possible, specify diagnosis, not individual symptoms. Record the name according to National Cancer Institute Common Terminology Criteria for Adverse Events (CTCAE) Version 5.0.
- Date of onset: Record the date of onset. Record approximate date if an actual date is unknown.
- Date of resolution: Record the date of resolution. Record approximate date if an actual date is unknown.
- Severity: Severity evaluation of adverse event must be done according to the NCI CTC grade.
  - The physician will use the following definitions of severity in accordance with the National Cancer Institute Common Terminology Criteria for Adverse Events (CTCAE) Version 5.0 to describe the maximum intensity of the adverse event:

Grade	Definition
Grade 1	Mild; asymptomatic or mild symptoms; clinical or diagnostic observations only; intervention not indicated.
Grade 2	Moderate; minimal, local or noninvasive intervention indicated; limiting age-appropriate instrumental ADL*.
Grade 3	Severe or medically significant but not immediately life-threatening; hospitalization or prolongation of hospitalization indicated; disabling; limiting self care ADL**.
Grade 4	Life-threatening consequences; urgent intervention indicated.
Grade 5	Death related to AE.

Activities of Daily Living (ADL)

\*Instrumental ADL refer to preparing meals, shopping for groceries or clothes, using the telephone, managing money, etc.

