\*\*Self care ADL refer to bathing, dressing and undressing, feeding self, using the toilet, taking medications, and not bedridden.

If the severity of an adverse event changed, the adverse event must be entered separately. Record stop date of previous severity and onset date of new severity – along with completion of all other items.

- Seriousness: Check either 'yes' or 'no'. If 'yes', record the appropriate number for the category of seriousness.

A serious adverse event is any untoward medical occurrence in a subject administered a medicinal or nutritional product (including pediatric formulas) at any dose that:

- (1) results in death;
- (2) is life-threatening;
- (3) requires inpatient hospitalization or prolongation of hospitalization;
- (4) results in persistent or significant disability/incapacity(substantial disruption of the ability to conduct normal life functions);
- (5) results in congenital anomaly/birth defect.

Progression of the malignancy under study (including signs and symptoms of progression) should not be reported as a serious adverse event unless the outcome is fatal within the safety reporting period. Hospitalization due to signs and symptoms of disease progression should not be reported as a serious adverse event. If the malignancy has a fatal outcome during the study or within the safety reporting period, then the event leading to death must be recorded as an adverse event and as a serious adverse event with severity Grade 5.

Lack of efficacy should be reported as an adverse event when it is associated with a serious adverse event.

Medical and scientific judgment is exercised in determining whether an event is an important medical event. An important medical event may not be immediately life-threatening and/or result in death or hospitalization. However, if it is determined that the event may jeopardize the subject or may require intervention to prevent one of the other outcomes listed in the definition above, the important medical event should be reported as serious.

Examples of such events are intensive treatment in an emergency room or at home for allergic bronchospasm; blood dyscrasias or convulsions that do not result in hospitalization; or development of drug dependency or drug abuse.

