Additionally, any suspected transmission via a Pfizer product of an infectious agent, pathogenic or non-pathogenic, is considered serious. The event may be suspected from clinical symptoms or laboratory findings indicating an infection in a subject exposed to a Pfizer product. The terms “suspected transmission” and “transmission” are considered synonymous. These cases are considered unexpected and handled as serious expedited cases by PV personnel. Such cases are also considered for reporting as product defects, if appropriate.

In case of serious adverse event, Drug Safety Unit in Pfizer Pharmaceuticals Korea is to be notified promptly by the physician.

Check the following at the end of the study or after the resolution of adverse event.

- Outcome: The evaluation of outcome will include: Record the date of recovery in case of ‘Recovered’ or ‘Recovered with sequelae’.
  - Recovered
  - Recovered with sequelae
  - Recovering
  - Not recovered
  - Unknown

- Causality of adverse event to the study drug: The causal relationship of adverse event to the study drug must be allocated by the physician according to the following criteria.

(1) Certain

- It follows a reasonable time sequence from administration of the drug (before and after the study medication).
- It could not be explained by other drugs, chemical substance or accompanying diseases.
- It has clinically reasonable reaction on cessation of the drug.
- It has pharmacological or phenomenological reaction to re-administration of the drug, where necessary.

(2) Probable/likely

- It follows a reasonable time sequence from administration of the drug (before and after the study medication).
- It could not be explained by other drugs, chemical substance or accompanying diseases.
- It has clinically reasonable reaction on cessation of the drug.

(No information on re-administration)

(3) Possible

- It follows a reasonable time sequence from administration of the drug.
- It could also be explained by other drugs, chemical substance or accompanying diseases.
- It lacks information or has unclear information on discontinuation of the drug.

(4) Unlikely

- It is not likely to have a reasonable causal relationship from administration of the drug. Rather, it seems to be temporary.
- It could also be reasonably explained by other drugs, chemical substances or latent diseases.

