6.2. Safety Analyses

Safety analyses will be performed based on data of safety analysis set. All adverse events in CRF will be classified by System Organ Class (SOC) and Preferred Term (PT) according to the latest version of Medical Dictionary for Regulatory Activities (MedDRA).

- 1) All adverse events investigated after administration of INLYTA® will be summarized with the number of subjects having adverse events, incidence of adverse events with 95% confidence interval (CI) and the number of adverse events by categorizing as follows.
 - Serious adverse events and serious adverse drug reactions
 - Unexpected serious adverse events and unexpected serious adverse drug reactions
 - Unexpected adverse events and unexpected adverse drug reactions
 - Adverse events and adverse drug reactions
- 2) All adverse events investigated after administration of INLYTA® will be summarized with the frequency and percentage of adverse events by categorizing as follows.

Statistical Analysis Plan for rPMS

- Occurrence status of adverse events by their severity
 - Grade 1 (Mild)
 - Grade 2 (Moderate)
 - Grade 3 (Severe or medically significant)
 - Grade 4 (Life-threatening consequences)
 - Grade 5 (Death related to AE)
- Occurrence status of adverse events by their outcome
 - Recovered
 - Recovered with sequelae
 - Recovering
 - Not recovered
 - Unknown
- Occurrence status of adverse events by their seriousness
 - SAE
 - Results in death
 - Is life-threatening
 - Requires inpatient hospitalization or prolongation of hospitalization
 - Results in persistent or significant disability/incapacity (substantial disruption of the ability to conduct normal life functions)
 - Results in congenital anomaly/birth defect
 - Other important medical event: if it is determined that the event may jeopardize the subject or may require intervention to prevent one of the other outcomes listed in the definition above
 - Non-SAE
- Occurrence status of adverse events by their causality to INLYTA®
 - Related to INLYTA®: ① Certain
 - ② Probable/likely
 - ③ Possible
 - ⑤ Conditional/unclassified
 - ⑥ Unaccessible/unclassifiable
 - ⑦ Not applicable
 - Not related to INLYTA®: ④ Unlikely
- Occurrence status of adverse events by their other causality (In case of 'not related to INLYTA®')
 - Disease under the study
 - Other diseases
 - Concomitant treatment drug or non-drug

Statistical Analysis Plan for rPMS

- Others
- Occurrence status of adverse events by action

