[Table 7] Administrative status for INLYTA®

Factor	Classification	Number of subjects n(%)
Period of first administration [†]	Sub-group 1	xxx(xx.xx)
	Sub-group 2	xxx(xx.xx)
	Total	xxx(xx.xx)
Duration of administration (day)	n	xxx
	Mean±SD	xx.xx±xx.xx
	Median	xx.xx
	Min~Max	xx.xx~xx.xx
	Category 1	xxx(xx.xx)
	Category 2	xxx(xx.xx)
	Category 3	xxx(xx.xx)
	...	xxx(xx.xx)
	Total	xxx(xx.xx)
Total dose (mg)	n	xxx
	Mean±SD	xx.xx±xx.xx
	Median	xx.xx
	Min~Max	xx.xx~xx.xx
Daily average dose (mg/day)	n	xxx
	Mean±SD	xx.xx±xx.xx
	Median	xx.xx
	Min~Max	xx.xx~xx.xx
	Category 1	xxx(xx.xx)
	Category 2	xxx(xx.xx)
	Category 3	xxx(xx.xx)
	...	xxx(xx.xx)
	Total	xxx(xx.xx)

[†]Sub-group 1: Subjects who are first administered INLYTA® during the study period

Sub-group 2: Subjects who has continued administration of INLYTA® since the time prior to the contract date

Dummy Table

[Table 8] Summary of incidence of adverse events

Adverse Events	Sub-group 1 (N=xxx) n(%), [E]	Sub-group 2 (N=xxx) n(%), [E]	Total (N=xxx) n(%), [E]
Serious adverse events	xxx(xx.xx), [xxx]	xxx(xx.xx), [xxx]	xxx(xx.xx), [xxx]
Serious adverse drug reactions	xxx(xx.xx), [xxx]	xxx(xx.xx), [xxx]	xxx(xx.xx), [xxx]
Unexpected serious adverse events	xxx(xx.xx), [xxx]	xxx(xx.xx), [xxx]	xxx(xx.xx), [xxx]
Unexpected serious adverse drug reactions	xxx(xx.xx), [xxx]	xxx(xx.xx), [xxx]	xxx(xx.xx), [xxx]
Unexpected adverse events	xxx(xx.xx), [xxx]	xxx(xx.xx), [xxx]	xxx(xx.xx), [xxx]
Unexpected adverse drug reactions	xxx(xx.xx), [xxx]	xxx(xx.xx), [xxx]	xxx(xx.xx), [xxx]
Adverse events	xxx(xx.xx), [xxx]	xxx(xx.xx), [xxx]	xxx(xx.xx), [xxx]
Adverse drug reactions	xxx(xx.xx), [xxx]	xxx(xx.xx), [xxx]	xxx(xx.xx), [xxx]

Sub-group 1: Subjects who are first administered INLYTA® during the study period

Sub-group 2: Subjects who has continued administration of INLYTA® since the time prior to the contract date

E: number of adverse events

Dummy Table

[Table 9] Serious adverse events and serious adverse drug reactions

System Organ Class [§] Preferred Term	Serious adverse events		Serious adverse drug reactions	
	n(%), [E]	[95% CI]	n(%), [E]	[95% CI]
System Organ Class Preferred Term	xxx(xx.xx), [xxx] xxx(xx.xx), [xxx] xxx(xx.xx), [xxx] xxx(xx.xx), [xxx]	[xx.xx, xx.xx] [xx.xx, xx.xx] [xx.xx, xx.xx]	xxx(xx.xx), [xxx] xxx(xx.xx), [xxx] xxx(xx.xx), [xxx]	[xx.xx, xx.xx] [xx.xx, xx.xx] [xx.xx, xx.xx]
Total	xxx(xx.xx), [xxx]	[xx.xx, xx.xx]	xxx(xx.xx), [xxx]	[xx.xx, xx.xx]

[§]Overlapped, MedDRA latest version

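### AE records split at each grade change are counted as separate AEs in the event-level tables, and no table counts the subjects who stopped because of an AE

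*Protocol*

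**What the plan says.** Protocol 3.5.4.9.1 (Adverse Event) gives two instructions on grade. The severity item asks for the CTCAE grade that reflects the greatest intensity the AE reached, which implies one grade per AE. Further on it says: "If the severity of an adverse event changed, the adverse event must be entered separately". Each entry has its own dates, "along with completion of all other items", so it is a full record with seriousness, outcome, causality and action. Outcome has its own timing: "Check the following at the end of the study or after the resolution of adverse event". For onset and resolution dates: "Record approximate date if an actual date is unknown".

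SAP 6.2 starts from the CRF entries: "All adverse events in CRF will be classified by System Organ Class (SOC) and Preferred Term (PT". Item 1 (Tables 8 to 15) reports "the number of subjects having adverse events, incidence of adverse events with 95% confidence interval (CI) and the number of adverse events". Item 2 (Tables 16 to 22) is by event only: "All adverse events investigated after administration of INLYTA® will be summarized with the frequency and percentage of adverse events by categorizing as follows". Table 8 defines its bracketed figure as "E: number of adverse events".

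Protocol 3.5.3.1 and SAP 4.1 both name discontinuation because of AEs as a safety endpoint. The action item in Protocol 3.5.4.9.1 and SAP 6.2 has a single discontinuation category covering permanent, temporary and delayed stops.

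**The concern.** One AE that changes grade becomes two or more complete records. Nothing in SAP 5, 6.2, 6.4 or 7, or in the notes to the dummy tables, links or collapses them. The overlap footnotes attached to the System Organ Class heading are not a linking rule. The event tables then depend on how often AEs changed grade as well as on how many occurred. Outcome is to be checked at resolution or study end, so the outcome that a superseded record carries into Table 17 is undefined.

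The second gap is separate. A reader of the final report will ask how many subjects stopped because of an AE. Table 22 counts events. Tables 10, 12 and 14 list action by subject, but only for serious or unexpected AEs and only in the re-examination report. A stop for an expected, non-serious AE appears in no subject-level output.

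The study's stated objective is to monitor use, including AEs, and severity, outcome, causality and discontinuation are named endpoints.

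**Working it through.** The plan has no figure to reproduce. It gives no grade-change rate, and the minimum of 100 subjects (Protocol 3.6) is regulatory.

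**Step 1: what each output counts.** An AE with k grade periods adds:
- k to [E] in Tables 8, 9, 11, 13, 15, 32 to 35 and 37, wherever its records qualify for the row;
- k to the totals of Tables 16 to 20 and 22, and to Table 21 if judged not related;
- 1 to the subject count, so n(%), its 95% CI and Tables 23 to 25 do not change.

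**Step 2: size of the repeat counting.** Assumptions, for illustration only: 100 subjects, one AE each; a share f of AEs changes grade, f = 10% to 30%; the other AEs are Grade 1 or 2. With c = 100f changing AEs, records = 100 + (k − 1)c.

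| Course | f | Records ([E]) | Excess | Table 16 peak-grade cell | By AE at maximum grade |
|---|---|---|---|---|---|
| 2-3-2 (k = 3) | 10% | 100 + 20 = 120 | 20% | Grade 3: 10/120 = 8.3% | 10% |
| 2-3-2 (k = 3) | 30% | 100 + 60 = 160 | 60% | Grade 3: 30/160 = 18.8% | 30% |
| 3-4 (k = 2) | 10% | 100 + 10 = 110 | 10% | Grade 4: 10/110 = 9.1% | 10% |
| 3-4 (k = 2) | 30% | 100 + 30 = 130 | 30% | Grade 4: 30/130 = 23.1% | 30% |

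In the 3-4 course the Grade 3 cell also shows 9.1% to 23.1%, against 0% by maximum grade. The Grade 3 percentage is thus too low in one course and too high in the other. Subjects with any AE stay at 100/100 throughout.

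**Step 3: Table 19.** Suppose 50 of the 100 AEs are related and the course is 2-3-2.
- All changing AEs related: (50 + 2c)/(100 + 2c) = 70/120 = 58.3% to 110/160 = 68.8%.
- None related: 50/(100 + 2c) = 50/120 = 41.7% to 50/160 = 31.3%.
- Related as often as the rest: (50 + c)/(100 + 2c) = 60/120 = 80/160 = 50%, no shift.

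**Step 4: discontinuation.** No rate or permanent/temporary split is given, so this gap cannot be sized. As an illustration, if 10 of 100 subjects stopped, a subject-level result would be 10% (exact 95% CI 4.9% to 17.6%). Table 22 would show 10, 20 or 30 events if each stop stood on 1, 2 or 3 AE records.

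**The case against.** Splitting records by grade is an ordinary way to collect AEs, and the SAP does not contradict the separate-entry rule: the protocol makes each grade period an entry and the SAP counts entries. Counts of grade periods can be interpreted if labelled as such, so a footnote naming the unit would answer part of the point. That stands. A footnote would not settle which outcome a superseded record carries, nor turn the percentages in Tables 16 to 22 into percentages of AEs.

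The CRF is not among the documents. It may hold a field linking records, or separate boxes for permanent and temporary stops. That also stands, but the SAP uses neither. The dummy Table 22 lost columns in text extraction, so pooling is read here from the wording of the protocol and SAP 6.2, not from the table layout.

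No passage promises subjects by worst grade, so that table would be an addition to the plan. The plan does name discontinuation as an endpoint, but does not promise it by subject or split by type of stop; Table 22 does report it in some form.

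A broad linking rule could do harm. If it also drove subject rows, taking an AE as serious or related when any record is, then among the 2 × 2 × 2 × 2 = 16 serious-by-related patterns of a two-record AE the serious adverse drug reaction (ADR) status would change in 2, where the serious record and the related record differ. Keeping the strongest causality would leave an AE related after a later judgement of Unlikely, although Protocol 5.1.3 refers to the investigator's final determination.

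**Conclusion.** The point holds, within limits. Followed as written, the plan counts one AE more than once in [E] and Tables 16 to 22 under a label that says AEs. Under the assumed 10% to 30% of AEs changing grade, [E] is 20% to 60% too high for a 2-3-2 course and 10% to 30% too high for a 3-4 course; the true size is unknown. The number of subjects who stopped because of an AE is not a planned result.

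Two stronger readings are tempting. A reader might infer that AE incidence is overstated; it is not, because a subject counts once however many records there are. A reader might also infer that relatedness in Table 19 is biased in a known direction; the shift can be up, down or nil, depending on which AEs change grade. For the same reason, readers of the report could not correct the tables themselves.

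This should be settled before database lock, but it does not threaten the main incidence results.

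**What to change.** 1. Reconcile the two grading instructions in Protocol 3.5.4.9.1. In SAP 6.2, link consecutive grade records of the same AE within a subject: same Preferred Term, with one record's stop date meeting the next one's onset. Review links before database lock where dates are approximate.
2. Count each linked AE once in every [E] and in Tables 16 to 22: maximum grade, final outcome, and the investigator's final causality assessment (used for Tables 19, 20 and 21 alike). Show seriousness and action under each category met, footnoted as overlapping.
3. Apply linking to event counts only. Leave all subject-level rows, including serious ADR and unexpected rows, derived from the records as now. Subject counts and [E] can then disagree in a combined row; footnote how many.
4. Add subjects n(%) with 95% CI for any AE leading to discontinuation, overall and by sub-group. Show permanent stops apart from temporary or delayed ones if the CRF records the difference; otherwise label the count as pooled.
5. Optionally, add subjects by worst grade, which needs no linking.

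Cost: protocol and SAP wording, modest programming and a limited manual review. Grades, dates, outcomes, causality and actions are already collected; new data would be needed only for a permanent/temporary split that the CRF does not hold. Some links will rest on approximate dates.

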## 5. MANAGEMENT AND REPORTING OF ADVERSE EVENTS/ADVERSE REACTIONS

### 5.1. Requirements for the study

#### 5.1.1. REQUIREMENTS

The table below summarizes the requirements for recording safety events on the case report form and for reporting safety events on the non-interventional study (NIS) adverse event monitoring (AEM) Report Form to Pfizer Safety. These requirements are delineated for three types of events: (1) serious adverse events (SAEs); (2) non-serious AEs (as applicable); and (3) scenarios involving drug exposure, including exposure during pregnancy, exposure during breast feeding, medication error, overdose, misuse, extravasation, and occupational exposure. These events are defined in the section “Definitions of safety events”.

Safety event	Recorded on the case report form	Reported on the NIS AEM Report Form to Pfizer Safety within 24 hours of awareness
SAE	All	All
Non-serious AE	All	None
Scenarios involving exposure to a drug under study, including exposure during pregnancy, exposure during breast feeding, medication error, overdose, misuse, extravasation; lack of efficacy; and occupational exposure	All (regardless of whether associated with an AE), except occupational exposure	All (regardless of whether associated with an AE)

For each AE, the investigator must pursue and obtain information adequate both to determine the outcome of the adverse event and to assess whether it meets the criteria for classification as a SAE (see section "Serious Adverse Events" below).

Safety events listed in the table above must be reported to Pfizer within 24 hours of awareness of the event by the investigator **regardless of whether the event is determined by the investigator to be related to a drug under study**. In particular, if the SAE is fatal or

life-threatening, notification to Pfizer must be made immediately, irrespective of the extent of available event information. This timeframe also applies to additional new (follow-up) information on previously forwarded safety event reports. In the rare situation that the investigator does not become immediately aware of the occurrence of a safety event, the investigator must report the event within 24 hours after learning of it and document the time of his/her first awareness of the events.

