## **5.2. DEFINITIONS OF SAFETY EVENTS**

### **5.2.1. Adverse events**

An AE is any untoward medical occurrence in a patient administered a medicinal product. The event need not necessarily have a causal relationship with the product treatment or usage. Examples of adverse events include but are not limited to:

- Abnormal test findings (see below for circumstances in which an abnormal test finding constitutes an adverse event);
- Clinically significant symptoms and signs;
- Changes in physical examination findings;
- Hypersensitivity;
- Lack of efficacy;

- Drug abuse;
- Drug dependency.

Additionally, for medicinal products, they may include the signs or symptoms resulting from:

- Drug overdose;
- Drug withdrawal;
- Drug misuse;
- Off-label use;
- Drug interactions;
- Extravasation;
- Exposure during pregnancy;
- Exposure during breast feeding;
- Medication error;
- Occupational exposure.

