### Lack of Efficacy

Reports of lack of efficacy to a Pfizer product are reported to Pfizer by the investigator, irrespective of the presence of an associated AE/SAE or the indication for use of the Pfizer product.

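### The protocol gives conflicting rules for when lack of efficacy is an adverse event, and the SAP has no rule for such records, so AE and ADR tables may include efficacy failure inconsistently

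*Protocol*

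**What the plan says.** Four places in the protocol deal with lack of efficacy.

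- Section 3.5.4.9.1, the instructions for the AE part of the CRF: "Lack of efficacy should be reported as an adverse event when it is associated with a serious adverse event".
- Section 5.2.1, the AE definition. Under the lead-in "Examples of adverse events include but are not limited to" one bullet reads "Lack of efficacy", without a condition. A second list in that section covers signs and symptoms that result from overdose, misuse, medication error and the like. Lack of efficacy is in the first list, not the second.
- Section 5.1.1, the requirements table. The exposure-scenario row includes "extravasation; lack of efficacy; and occupational exposure". Its CRF entry and its 24-hour reporting entry both begin "All (regardless of whether associated with an AE". Only occupational exposure is exempt from the CRF.
- Section 5.2.3, under its lack-of-efficacy heading. Cases go to the sponsor "irrespective of the presence of an associated AE/SAE or the indication for use of the Pfizer product".

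Progression of the malignancy has its own paragraph in 3.5.4.9.1, repeated in 5.2.2: it "should not be reported as a serious adverse event unless the outcome is fatal within the safety reporting period". Fatal progression must be recorded as an AE and as a Grade 5 SAE. Neither section says whether non-fatal progression is a non-serious AE.

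SAP 6.2 classifies and summarises all AEs on the CRF. It has no rule for lack-of-efficacy or progression records. For causality it treats only Unlikely as not related. Not applicable and the two unclassified categories are grouped as related.

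**The concern.** The same event meets the AE definition in 5.2.1 unconditionally, but the CRF instruction in 3.5.4.9.1 attaches a condition. A site that follows one section will enter records that a site following the other will not, and both can cite the protocol. The SAP then counts whatever was entered.

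The study objective in Protocol section 2 is to monitor use of the drug, including adverse events, so AE and ADR incidence are central outputs. If some sites log efficacy failure as an AE, three kinds of result are exposed:

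- AE incidence and event counts in Tables 8 and 15, and the event breakdowns in Tables 16 to 22.
- ADR counts, where such a record carries a causality of not applicable.
- The factor tests and logistic regression in Tables 23 to 25, whose response is the occurrence of any AE. Predictors of treatment failure could appear there as predictors of toxicity.

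Efficacy failure is already analysed in SAP 6.3 as best overall response, ORR, PFS and TTP.

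**Working it through.** **Comparison of the texts**

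| Section | Condition for lack of efficacy | Where it goes |
|---|---|---|
| 3.5.4.9.1 | Associated with an SAE | AE section of the CRF |
| 5.2.1 | None | Meets the AE definition |
| 5.1.1 | None | CRF (part not stated), and sponsor within 24 hours |
| 5.2.3 | None | Sponsor |

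Sections 5.1.1 and 5.2.3 can be squared with 3.5.4.9.1 if lack of efficacy is a reporting scenario distinct from an AE. Section 5.2.1 cannot, because it names lack of efficacy as an AE. Section 5.1.1 leaves open which part of the CRF takes the record, and that decides whether SAP 6.2 counts it.

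**Illustration of size**

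The documents give no AE or progression rates, so there is no plan figure to reproduce. All rates below are assumptions. The only input from the documents is the minimum of 100 patients (Protocol 3.6).

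Let *p0* be the share of patients with any other AE and *pp* the share with non-fatal progression recorded as lack of efficacy. Fatal progression within the reporting period is an AE in either case and is left out of *pp*. With independence:

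- any-AE incidence when these records are counted = 1 − (1 − *p0*)(1 − *pp*)
- rise over *p0* = (1 − *p0*) × *pp*

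| *p0* | *pp* | Any-AE incidence | Rise (points) |
|---|---|---|---|
| 70% | 30% | 1 − 0.30 × 0.70 = 79% | 9 |
| 70% | 80% | 1 − 0.30 × 0.20 = 94% | 24 |
| 80% | 30% | 1 − 0.20 × 0.70 = 86% | 6 |
| 80% | 80% | 1 − 0.20 × 0.20 = 96% | 16 |
| 95% | 30% | 1 − 0.05 × 0.70 = 96.5% | 1.5 |
| 95% | 80% | 1 − 0.05 × 0.20 = 99% | 4 |

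Without independence, the rise still cannot exceed 1 − *p0*: 5 points at 95% and 30 points at 70%.

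These figures compare all sites under one rule with all sites under the other. If sites holding a fraction *f* of patients enter the records, with the same rates at all sites, the rise is multiplied by *f*. At *f* = 0.5 it is 0.75–2 points for *p0* = 95% and 4.5–12 points for *p0* = 70%.

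The preferred-term row is more sensitive, because it does not depend on *p0*. With 100 patients it goes from 0% (exact 95% CI 0–3.6%) to 30% (21.2–40.0%) at *pp* = 30% and to 80% (70.8–87.3%) at *pp* = 80%.

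**The case against.** The strongest reply is that the conflict comes down to one bullet. Section 3.5.4.9.1 says when, not only when. Sections 5.1.1 and 5.2.3 describe a separate reporting route that can coexist with it, and 5.2.1 is a general list of examples. The point about 5.1.1 and 5.2.3 stands. The rest does not remove the conflict: if lack of efficacy were always an AE, the condition in 3.5.4.9.1 would have no function, and the bullet in 5.2.1 sits inside the AE definition itself.

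The second reply is that lack of efficacy is not progression. This stands. No section equates them: 3.5.4.9.1 treats them in separate paragraphs, and progression is captured through RECIST assessments. For an anticancer drug the link is a fair inference, since no section rules it out, but it remains an inference. A reader might infer that sites will log ordinary progression as a non-serious AE. The documents do not show that they will.

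The third reply concerns ADRs. The protocol offers the disease under study as an alternative cause for events unrelated to the drug, and SAP 6.2 maps Unlikely to not related. Records coded that way stay out of the ADR counts. This also stands. The ADR tables are exposed only through records coded to a category that the SAP groups as related, such as not applicable.

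**Conclusion.** Wrong as written, to a limited extent. The protocol sets different conditions for the same event, and the SAP does not settle how the resulting records are tabulated. AE and ADR tables may therefore include efficacy failure inconsistently between sites.

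The size is unknown. With progression in 30–80% of patients, independence, and every such case recorded under one rule and none under the other, any-AE incidence differs by about 1.5–4 points if 95% of patients have another AE and by 9–24 points if 70% do. The preferred-term rows and event counts are more exposed than the overall rate. SAE incidence should be little affected, because 3.5.4.9.1 and 5.2.2 give the same rule for progression.

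A reader might infer that overall AE incidence will be inflated by 20 points or more. That needs a low rate of other AEs, frequent progression, progression logged as lack of efficacy, and near-complete recording. The documents establish none of these.

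**What to change.** 1. Reconcile Protocol 3.5.4.9.1, 5.1.1, 5.2.1 and 5.2.3 into one recording rule for lack of efficacy, naming the part of the CRF that takes the record. State whether non-fatal progression is to be entered as a non-serious AE.
2. In SAP 6.2, identify lack-of-efficacy and non-fatal progression records by preferred term, and present AE and ADR incidence with and without them. State which version is the response in Tables 23 to 25.
3. Apply this to data already collected. Collection began in December 2012 (Protocol Appendix 3), and new protocol wording cannot change earlier records. Incidence without these records is the more useful figure for that period, because it does not depend on which section a site followed.
4. Keep fatal progression in the AE and SAE tables. Protocol 3.5.4.9.1 and 5.2.2 require it as a Grade 5 SAE, and SAP 6.3 takes the date of death from that record. Excluding all progression terms would remove these deaths.

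The cost is wording in four protocol sections, a short addition to SAP 6.2, and a few more rows in the AE summary tables, repeated by sub-group.
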